# 2. STUDY OBJECTIVES

# 2.1. Primary Objective

The primary objective is to assess the reduction of allergic symptoms as measured by combined symptom and medication score (CSMS) during birch pollen season after a single dose of REGN5713-5714-5715 versus placebo.

# 2.2. Secondary Objectives

The secondary objectives are:

- To assess the reduction of allergic symptoms and use of allergy-relieving medications after a single dose of REGN5713-5714-5715 versus placebo, as measured by the total symptom score (TSS), total nasal symptom score (TNSS), total ocular symptom score (TOSS), and daily medication score (DMS)
- To evaluate the safety and tolerability of REGN5713-5714-5715, including the incidence of hypersensitivity reactions and local injection site reactions
- To evaluate the reduction in early allergic response to birch allergen after a single dose of REGN5713-5714-5715 versus placebo, as measured by SPT mean wheal diameter
- To determine systemic exposure of total antibody (ie, free and antigen-bound) in the form of concentration of REGN5713, REGN5714, and REGN5715 in serum
- To assess the immunogenicity to REGN5713, REGN5714, and REGN5715 in subjects after a single dose of REGN5713-5714-5715
- To evaluate "well days"

*Note: "Well days" are defined as days when the TSS is*  $\leq 2$  *without the use of anti-allergy rescue medications.* 

# 2.3. Exploratory Objectives

The exploratory objectives are:

- To assess asthma control as measured by the asthma control questionnaire (ACQ-5)
- To assess quality of life as measured by the rhinoconjunctivitis quality of life questionnaire (RQLQ [S])
- To evaluate the reduction in early allergic response to birch homologous allergens (alder and oak) as measured by SPT mean wheal diameter
- To assess the relationship between allergy sensitization status to Bet v 1 or birch pollen at screening (as measured by serum allergen specific-IgE [sIgE]) and clinical response to REGN5713-5714-5715 treatment
- To assess serum sIgE levels against Bet v 1 and birch pollen during birch pollen season to evaluate the relationship between the response to REGN5713-5714-5715 and change in sIgE levels in-season
- To assess the inhibitory effect of REGN5713-5714-5715 on the binding of endogenous serum IgE to birch allergen in an in vitro assay; to assess whether the degree of inhibition correlates with clinical improvement
- To assess sIgE levels against other allergens (eg, Bet v 2, alder and oak) at screening and to evaluate the relationship between response to REGN5713-5714-5715 and polyallergic status

**Regeneron Pharmaceuticals, Inc.** 

- To assess additional subclasses of serum antibodies (eg, total IgG and IgG4 against birch pollen and Bet v 1) to evaluate the relationship between endogenous anti-Bet v 1 antibodies and response to REGN5713-5714-5715
- To assess the reduction in PFAS and related symptoms as measured by pollen food allergy symptom questionnaire (PFASQ)
- To assess patient rating of severity of seasonal allergy symptoms as measured by patient global impression of severity (PGI-S)

# **3. HYPOTHESIS AND RATIONALE**

# 3.1. Hypothesis

A single SC dose of REGN5713-5714-5715 is more effective than placebo in the reduction of CSMS during birch pollen season.

Refer to Section 11.1 for the statistical hypothesis.

# 3.2. Rationale

## 3.2.1. Rationale for Study Design

### Study design and duration

This is a phase 3 multi-center, randomized, double-blind, placebo-controlled, parallel group study to assess the efficacy of anti-Bet v 1 mAbs (REGN5713-5714-5715) to reduce allergic rhinitis and conjunctivitis during birch pollen season. The study will last approximately 28 weeks, including screening (refer to Table 1 for a schedule of events). The actual duration of the study will vary depending on the start, peak, and end dates of the local birch pollen season for each study site, which will be variable across different geographies (refer to Section 9.2.2):

- Screening: Generally healthy male and female subjects 18 years and older with a history of birch allergy for at least 2 years will undergo screening visits before the onset of the birch pollen season. Subjects will be asked to refrain from taking specific prohibited medications within the specified period preceding screening (refer to Section 8.9.1).
- **Randomization**: Candidate subjects who meet all inclusion and no exclusion criteria will be randomized and receive the study drug. Randomization will be stratified based on geographical regions and sIgE levels at screening (refer to Section 8.5).
- **In-season visits**: Approximately 1 month after randomization (timing will vary based on the local pollen season), a telephone contact will occur to collect any AEs and concomitant medication information. There will be an in-clinic visit at the anticipated local peak of birch pollen season. An additional telephone contact will occur at the end of the local birch pollen season. An in-clinic visit will occur at the end of the study. Subjects will be asked to stop using specific rescue medications within 5 days of the end of study visit (refer to Section 8.9.1).

#### Efficacy measurements

Subjects will record symptom scores (TNSS, TOSS) daily. Subjects will be provided with rescue medications to treat allergic symptoms during the study (refer to Section 8.2) to treat their allergic rhinitis with or without conjunctivitis. Subjects will be asked to record their daily use of rescue medications using an e-diary throughout the birch pollen season to calculate the DMS. TNSS and TOSS are scored for a combined TSS. The TSS and DMS are combined for the CSMS.

ACQ-5 will be completed weekly to assess asthma control in asthmatic subjects. To assess subject quality of life, RQLQ (S) will be assessed weekly in all subjects. In addition, PFASQ and PGI-S will be administered throughout the study to assess treatment effects on PFAS symptoms and overall patient impression of severity. Refer to Section 9.2.4 for more details on these efficacy measures.

#### Primary objective

The primary objective of the study is to assess the reduction of allergic symptoms as measured by CSMS during birch pollen season after a single dose of REGN5713-5714-5715 versus placebo. The primary endpoint is CSMS, averaged over the duration of the birch pollen season, in subjects who receive a single dose of REGN5713-5714-5715 versus placebo. Based on recent reviews of SLIT products, for registration, the Food and Drug Administration (FDA) expects a treatment to reduce average CSMS by at least 15% compared to placebo. The European Medicines Agency (EMA) has a set a similar standard (approximately 20% compared to placebo) based on guidance from the World Allergy Organization (WAO) task force (Canonica, 2014). As CSMS is the recommended endpoint for in-field studies for allergic rhinitis treatments, this study will provide data on the treatment effect of REGN5713-5714-5715 on the CSMS.

#### Secondary objectives

A secondary objective of the study is to evaluate the average TSS, TNSS, TOSS, and DMS during birch pollen season comparing subjects who receive a single dose of REGN5713-5714-5715 versus placebo.

Incidence rates of treatment-emergent AEs (TEAEs) and serious TEAEs, as well as hypersensitivity reactions and local injection site reactions, will be collected to determine safety and tolerability of REGN5713-5714-5715.

Total concentration of REGN5713, REGN5714, and REGN5715 in serum will be assessed to determine systemic exposure of total antibody (ie, free and antigen-bound) throughout the study. In addition, immunogenicity to REGN5713, REGN5714, and REGN5715, as determined by the incidence, titer and clinical impact of treatment-emergent ADA responses will be assessed.

"Well days" will also be assessed. Well days are defined as days when rescue medication is not utilized and the TSS is  $\leq 2/18$ . This exploratory objective will provide information about the number of days a patient is not affected by their allergic rhinitis symptoms.

#### **Exploratory objectives**

Sensitization to birch and birch homologous group (alder and oak) will be assessed by SPT at screening and after a single 900 mg SC dose of REGN5713-5714-5715 or placebo.

Because these anti-Bet v 1 mAbs target Bet v 1 specifically, exploratory objectives will assess whether their efficacy is related to baseline levels of specific IgE to birch and Bet v 1. As it is known that allergen-specific IgE (sIgE) levels increase during the natural pollen season, other exploratory objectives are to determine whether efficacy is related to changes in birch and Bet v 1 sIgE. In addition, allergen sensitization to a panel of allergens, including but not limited to alder and oak, will be determined by baseline serum sIgE (cutoff value 0.35 kUa). Also, of interest is whether the treatment response is associated with circulating levels of anti-birch or anti-Bet v 1 IgG and IgG4. The regional SPT panel and sIgE panel that is performed before dosing will be analyzed to understand whether allergen sensitization to non-birch allergens is associated with treatment effect during birch pollen season.

Local tree pollen counts will be obtained to assess whether the efficacy of the anti-Bet v 1 antibody cocktail is associated with non-birch trees or other plants that may be pollinating at similar times as birch.

#### **3.2.2.** Rationale for Dose Selection

The proposed doses for this study are based on the results of Part B of the phase 1b POC, first-inhuman (FIH) study, which was conducted in healthy, birch-allergic subjects. In that study, a single dose of 900 mg SC REGN5713-5714-5715 (300 mg per mAb) resulted in a significant reduction in allergic rhinitis symptoms following a nasal allergen challenge for at least 2 months post-dose. Additionally, reduction in SPT-induced skin reaction was maintained for approximately up to 4 months post-dose in healthy subjects who were allergic to birch pollen. This dose was well-tolerated, with TEAEs generally of a mild to moderate severity, and occurred in similar rates in the placebo and REGN5713-5714-5715 treatment groups.

REGN5713-5714-5715 exhibited linear PK. Throughout the duration of the study, the concentration of total REGN5713-5714-5715 in serum was maintained above 10 mg/L, which had been identified from preclinical testing in the mouse percutaneous anaphylaxis (PCA) model as the concentration above which response to Bet v 1 was fully blocked.

Based on the above summary of safety, PK, and PD data, a single 900 mg SC dose of REGN 5713-5714-5715 (300 mg per mAb) is expected to prevent allergic symptoms and reduce the need for rescue medication for the duration of birch pollen season. Additional information on clinical and preclinical PK, PD, and safety can be found in the Investigator's Brochure.

#### 3.2.3. Rationale for the Selected Anti-Bet v 1 Monoclonal Antibody Cocktail

Preclinical studies were conducted to determine the optimal combination of anti-Bet v 1 mAbs REGN5713, REGN5714, and REGN5715. In addition to binding assays showing simultaneous, non-competitive binding to Bet v 1, a BAT using peripheral blood mononuclear cells (PBMCs) from birch-allergic donors showed near complete blocking efficacy using the 3-mAb cocktail. Specifically, when REGN5713-5714-5715 were added as a cocktail, there was 97% median blocking of Bet v 1-induced basophil activation with  $\geq$ 90% blockade observed in 9 of 10 donors tested. The single antibodies (REGN5713, REGN5714, and REGN5715) achieved a median of 50%, 55%, and 67% blocking, respectively, reaching  $\geq$ 90% blockade in only  $\leq$ 2 of 10 donors.

Regeneron has developed other mAbs against exogenous targets, including REGN1908 and REGN1909 (for Fed d 1); REGN10933 and REGN10987 (for SARS-CoV-2); atoltivimab, odesivimab, and maftivimab (for Ebola); REGN3048 and REGN3051 (for MERS-CoV), and suptavumab (for respiratory syncytial virus [RSV]). These mAbs demonstrated specificity to their exogenous targets with no significant safety findings and low incidence of hypersensitivity, injection site reactions, or immunogenicity. Similarly, REGN5713-5714-5715 was generally well-tolerated in the FIH study. In Part B of the FIH study, the overall frequency of treatment-related TEAEs was comparable between REGN5713-5714-5715 (21.9%) and placebo (25.0%), all of which were of mild or moderate intensity and resolved without sequalae. There were no SAEs or AEs leading to study discontinuation/death.

# 3.3. Risk-Benefit

REGN5713-5714-5715 has been administered as a single dose to 56 healthy adult subjects (24 without known birch allergy and 32 with known birch allergy) in a FIH study with no significant clinical safety findings observed. No important identified risks have been established with REGN5713-5714-5715. In birch-allergic subjects, a significant reduction in TNSS following a nasal allergen challenge was demonstrated through day 57, and a durable reduction in SPT response to birch was demonstrated through day 113. A potential benefit for subjects in this study and future patients may be to have an effective, rapid, and convenient therapeutic option with a favorable safety profile to prevent and treat birch-related allergic rhinitis. In a nonclinical toxicology study conducted in monkeys, REGN5713-5714-5715 was well tolerated at significantly higher doses than are planned for clinical evaluation.

As with most other protein therapeutics that are administered SC, mild or moderate injection site reactions may occur and may be treated symptomatically. Allergy/hypersensitivity reactions may develop; the most concerning are those that may develop immediately or within a few hours of administration of REGN5713-5714-5715. Because REGN5713-5714-5715 is composed of antibodies whose sequence is fully human, the risk of these immediate reactions is considered to be extremely low. Emergency equipment and medication for the treatment of these potential adverse effects (including but not limited to antihistamines, corticosteroids, acetaminophen, and/or epinephrine) are available for immediate use in this study. Considering the safety data and the exogenous nature of the target antigen, the risk of other adverse reactions is considered to be extremely low. A risk-benefit statement with respect to the overall development program is provided in the Investigator's Brochure.

A Safety Monitoring Team (SMT) will monitor blinded safety data on an ongoing basis to assess the risk-benefit profile of REGN5713-5714-5715 (refer to Section 6.3.1). Additionally, an Independent Data Monitoring Committee (IDMC) will be involved in the review of unblinded data in an ongoing manner (refer to Section 6.3.2).

Recognizing that the Coronavirus Disease 2019 (COVID-19) pandemic will have an impact on the conduct of clinical trials, the Sponsor does not intend to screen any patients in this study until the impact of the COVID-19 pandemic is deemed manageable and no longer interfering with the conduct of trials at individual sites, and patients can safely participate in this study. Until then, the Sponsor plans to obtain approvals from Health Authorities/Ethics Committees to enable initiation of study sites for this study, as allowed by local laws and regulations.

# 4. ENDPOINTS

# 4.1. Primary Endpoint

The primary endpoint is the daily CSMS, averaged over the duration of the birch pollen season, in subjects who receive a single dose of REGN5713-5714-5715 versus placebo.

# 4.2. Secondary Endpoints

The secondary endpoints are:

- TSS, TNSS, and TOSS, averaged over the duration of the birch pollen season, in subjects who receive a single dose of REGN5713-5714-5715 versus placebo
- DMS, averaged over the duration of the birch pollen season, in subjects who receive a single dose of REGN5713-5714-5715 versus placebo
- Incidence of TEAEs and serious TEAEs throughout the study
- Change and percent change from baseline to the end of study in birch SPT mean wheal diameter in subjects who receive a single dose of REGN5713-5714-5715 versus placebo
- Total REGN5713, REGN5714, and REGN5715 concentration in serum over the study duration
- Incidence of treatment emergent anti-drug antibodies (ADAs) to REGN5713, REGN5714, or REGN 5715 throughout the study
- The number of "well days" in each of the treatment groups, where the "well days" are defined as days when rescue medication is not utilized and the TSS is  $\leq 2/18$

# 4.3. Exploratory Endpoints

The exploratory endpoints are:

- ACQ-5, averaged over the duration of the birch pollen season, for REGN5713-5714-5715 versus placebo
- RQLQ (S), averaged over the duration of the birch pollen season, for REGN5713-5714-5715 versus placebo
- Change and percent change from baseline to the end of study in SPT mean wheal diameter for birch homologous/cross-reactive allergens in REGN5713-5714-5715 versus placebo
- Baseline allergen-specific IgE levels and correlation with average CSMS, TSS, TNSS, TOSS, DMS during birch pollen season
- Change and percent change from baseline to the peak of birch pollen season in allergenspecific IgE
- Change in inhibitory effect on serum IgE to birch allergen
- Number of baseline sensitizations to other allergens (poly/mono-sensitization status, based on allergen-specific IgE levels) and correlation with CSMS, TSS, TNSS, TOSS, and DMS, averaged over the duration of the birch pollen season
- Baseline serum antibody levels and correlation with CSMS, TSS, TNSS, TOSS, and DMS, averaged over the duration of the birch pollen season
- To assess the reduction in PFAS and related symptoms, as measured by PFASQ, from baseline to end of study
- To assess patient rating of severity of seasonal allergy symptoms, as measured by PGI-S, from baseline to end of study

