#### 9.1.1. Footnotes for the Schedule of Events Table

- Screening SPT for birch, birch homologous trees, and other common allergens will be performed as described in the study manual. Skin prick test for birch should be performed prior to other screening assessments. If screening SPT for birch is negative (ie, mean wheal diameter <5 mm greater than a negative control), then other screening visit procedures do not need to be performed as the subject will have failed screening (refer to Section 7.2.1 Inclusion Criteria, #3).
- 2. Randomization may occur within 1 day prior to study drug administration. All safety assessments performed at screening must be normal and checked against the inclusion/exclusion criteria prior to study drug administration.
- 3. The timing of in-clinic visits may vary for each study site, depending on the start, peak, and end dates of the local birch pollen season (as determined by local pollen counts; refer to Section 9.2.2). The randomization visit will be scheduled approximately 2 weeks before the start of birch pollen season, and the end of study (EOS) visit approximately 16 weeks after the randomization visit (depending on the duration of the local birch pollen season). In addition, visit 5 will be scheduled to occur within 2 weeks of the anticipated local peak of the birch pollen season.
- 4. If randomization occurs >60 days after the screening visit, medical history, blood chemistry, hematology, and spirometry must be repeated prior to randomization.
- 5. E-diary and rescue medications will be dispensed at the randomization visit. E-diary and any unused rescue medications will be returned at the EOS visit. Refer to Section 8.2 for more information on rescue treatments.
- 6. TNSS, TOSS, and DMS will be recorded daily via e-diary, starting at the randomization visit until EOS. Refer to Section 9.2.4.1, Section 9.2.4.2, and Section 9.2.4.4 for procedural details.
- 7. In asthmatic subjects, ACQ-5 scores will be recorded weekly via e-diary, starting from the randomization visit until EOS. Refer to Section 9.2.4.6 for procedural details.
- 8. In all subjects, RQLQ (S) scores will be recorded weekly via e-diary starting from the randomization visit until EOS. Refer to Section 9.2.4.7 for procedural details. In asthmatic subjects, the weekly RQLQ (S) and ACQ-5 assessments may be performed on the same day.
- 9. Refer to for Section 9.2.4.8 procedural details.
- 10. Refer to for Section 9.2.4.9 procedural details.

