#### 9.2.4.9. Patient Global Impression of Severity

The PGI-S assesses the severity of seasonal allergy symptoms over the past 1 week. Symptom severity ranges from 0 (no symptoms), 1 (mild), 2 (moderate), and 3 (severe) symptoms.

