## **11.4.3.3.** Exploratory Efficacy Analysis

Exploratory efficacy endpoints, including the average ACQ-5, RQLQ (S), and PGI-S scores during the birch pollen season will be analyzed in the same fashion as the primary analysis for the subjects receiving REGN5713-5714-5715 versus placebo. Subjects with at least 1 day of data will be included in the analysis.

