#### **Definition of baseline**

The last assessment before the administration of study drug on day 1 will be considered as the baseline evaluation.

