5.6.5. Analysis of Exploratory Efficacy Variables

For continuous exploratory efficacy variables, e.g. average ACQ-5 and change and percent change in SPT mean wheal diameter for birch homologous/cross-reactive allergens, they will be analyzed by using a linear mixed effects model similar to the analyses of primary endpoint.

For categorical exploratory variables, e.g. PFASQ and PGI-S, only descriptive summary will be provided.

For endpoints related to biomarker, e.g. serum total IgE, serum sIgE for birch and Bet v 1, analysis method will be detailed in section 5.11.

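### At nominal timing the exploratory PGI-S endpoint compares a pre-season with a post-season rating, and the protocol and SAP disagree on how PGI-S is analysed

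*Protocol*

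**What the plan says.** Protocol 4.3 lists the endpoint as "To assess patient rating of severity of seasonal allergy symptoms, as measured by PGI-S, from baseline to end of study"; SAP 4.5.3 repeats it. Protocol 9.2.4.9 sets the recall: "The PGI-S assesses the severity of seasonal allergy symptoms over the past 1 week", scored 0 to 3.

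On timing, protocol 11.5 takes the last pre-dose value as baseline, and footnote 3 in protocol 9.1.1 says "The randomization visit will be scheduled approximately 2 weeks before the start of birch pollen season". The same footnote puts the end-of-study (EOS) visit about 16 weeks after randomization, depending on the local season, and puts Visit 5 within 2 weeks of the anticipated local peak. Protocol 3.2.1 adds: "An additional telephone contact will occur at the end of the local birch pollen season". Table 1 schedules PGI-S at Visits 2, 5 and 7.

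On analysis, protocol 11.4.3.3 covers exploratory endpoints "including the average ACQ-5, RQLQ (S), and PGI-S scores during the birch pollen season", to be handled like the primary analysis. SAP 5.6.5 says that for categorical variables such as PGI-S "only descriptive summary will be provided".

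**The concern.** PGI-S is meant to capture how severe patients judge their seasonal symptoms to be, and protocol 3.2.1 says it is there to assess treatment effects. Read as a two-point contrast, the endpoint uses one rating from before the pollen arrives and one that will usually come after it has gone. With a 1-week recall, neither would normally describe a week of birch exposure.

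The EOS rating has two further complications. Protocol 8.2 and 8.9.1 ask subjects to do without desloratadine and olopatadine for the 5 days before EOS, so most of the recall week falls under a different rescue condition from the season itself. Protocol 11.5 also recognises that grass pollen may follow birch and excludes symptom and medication data once the grass season starts, without saying whether PGI-S is covered.

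At stake is whether this exploratory objective can be answered from a pre-specified comparison. If it is not settled before unblinding, an uninformative EOS summary could be taken as absence of patient-perceived benefit, and any in-season PGI-S result could look like a choice made afterwards.

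**Working it through.** The documents give no effect size, SD or power for PGI-S, so there is no plan figure to reproduce. The check is day arithmetic, followed by a comparison of the specifications.

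**Inputs**
- Season start: about 2 weeks after randomization on day 1, so 1 + 14 = day 15 (protocol 9.1.1, footnote 3).
- Season-end contact: taken to be Visit 6, day 85 ± 14 (protocol 3.2.1 and Table 1). Linking the two is an inference; Visit 6 is the telephone contact between the peak visit and EOS.
- EOS: Visit 7, day 113 ± 14. Visit 5: day 57 ± 14 (Table 1).
- Recall: 7 days (protocol 9.2.4.9).

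**Formulas**
- Start of recall week = visit day − 7.
- Gap = start of recall week − last day of season. A negative gap means overlap.
- Season length needed to reach the recall week = start of recall week − 15 + 1.

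| EOS day | Recall starts | Season length needed | Gap, season ends day 71 | Gap, day 85 | Gap, day 99 |
|---|---|---|---|---|---|
| 99 (earliest) | 92 | 78 days | 21 | 7 | −7 |
| 113 (nominal) | 106 | 92 days | 35 | 21 | 7 |
| 127 (latest) | 120 | 106 days | 49 | 35 | 21 |

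A season ending on day 85 lasts 85 − 15 + 1 = 71 days, against the 92 needed to reach the nominal EOS recall week. Within the windows, overlap appears only when a late season end meets an early EOS. The interval from season-end contact to EOS is nominally 113 − 85 = 28 days, and can run from 99 − 99 = 0 to 127 − 71 = 56 days.

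**The in-season rating.** At Visit 5 the recall week starts on day 57 − 7 = 50, with a range from 43 − 7 = 36 to 71 − 7 = 64. All of these lie inside a season running from day 15 to day 85.

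**Early termination.** The EOS column of Table 1 also serves early termination. Under SAP 6.4, an early-termination PGI-S on days 2 to 85 is mapped to Visit 5 if that value is missing, and to Visit 7 if it is present. A few Visit 5 values could therefore be pre-season, and a few Visit 7 values in season.

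**Specifications side by side**

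| Place | Time point | Method |
|---|---|---|
| Protocol 4.3, SAP 4.5.3 | Baseline to EOS | Not stated |
| Protocol 11.4.3.3 | Average during the season | As primary (linear mixed model) |
| SAP 5.6.5 | Not stated; SAP 6.4 gives windows for Visits 5 and 7 | Descriptive only |

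Visit 5 is the only scheduled PGI-S visit placed in season, so the protocol's in-season average is in practice that one value. SAP 1.2.3 lists only the removal of the per-protocol set as a departure from the protocol; the move from a model to description is not there.

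**Illustration by assumption.** Suppose a two-sided 5% comparison had 90% power for the in-season effect, and the EOS contrast kept a fraction f of that effect with the same SD. Power is then about Φ(3.242f − 1.960) + Φ(−3.242f − 1.960), where 3.242 = 1.960 + 1.282. For f = 0, 0.25, 0.50 and 0.75 this gives 5%, 13%, 37% and 68%. The documents do not say what f is, so this is a range and not an estimate.

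**The case against.** The other side has four fair arguments.

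- **The line may not define a contrast.** The skin prick test and sIgE items in protocol 4.3 speak of change and percent change; the PGI-S item does not. It could mean the span over which PGI-S is followed, and protocol 3.2.1 does say it is given throughout the study. The ambiguity is real, but an endpoint open to two readings still needs settling.
- **The in-season value is not ignored.** Protocol 11.4.3.3 plans to analyse it, and SAP 6.4 gives PGI-S a Visit 5 window, so a by-visit descriptive summary would include the near-peak rating. This stands. A reader might infer that the plan discards the in-season data; the documents do not support that.
- **The timing is not fixed.** A reader might infer that the endpoint cannot show a treatment effect. That goes too far. EOS moves with the local season and has a ±14-day window, some early-termination ratings map to Visit 7, and the item asks about seasonal allergy symptoms, not birch symptoms alone.
- **No formal null result can arise.** The SAP plans no PGI-S test, so a failed test caused by timing is not a risk as the SAP is written. This also stands. What remains is the risk of misreading a descriptive summary.

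In-season burden is also measured by the daily scores, weekly RQLQ (S) and well days, which limits what is lost.

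**Conclusion.** The point holds in a limited form. Read as a baseline-to-EOS contrast, the PGI-S endpoint is insensitive to a birch-season effect at nominal timing, because the EOS recall week begins about 21 days after the season-end contact. This assumes that the season starts near day 15, that the season-end contact is Visit 6 on day 85, and that EOS is on day 113. Within the Table 1 windows, the gap for a day-85 season end runs from 7 to 35 days; overlap needs a later season end together with an early EOS.

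The firmer part of the finding needs no timing assumption: the endpoint text, the protocol analysis and the SAP analysis do not agree, and the SAP does not record the change.

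The consequence is small. PGI-S is exploratory and absent from the hierarchy in SAP 5.6.3, so the primary conclusion and the sample size are untouched.

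**What to change.** Before database lock and code breaking, which SAP section 1 allows:

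1. Define the endpoint as PGI-S at Visit 5, and check each rating's recall week against the site's season dates in SAP 4.10. Say how a rating outside the season is handled, including an early-termination value mapped into the Visit 5 window.
2. Compare the arms with adjustment for the stratification factors and baseline PGI-S. An ordinal model would suit a 0-to-3 item that the SAP already treats as categorical.
3. Keep the EOS rating as a descriptive value, and state whether the grass-season exclusion applies to PGI-S.
4. Align protocol 4.3 and 11.4.3.3 with SAP 4.5.3 and 5.6.5, and log the change in SAP 1.2.3.

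No new visit or data item is needed. The cost is wording and a little extra analysis. Visit 5 follows the anticipated peak and not the observed one, so some ratings may miss the actual season and the number contributing may be smaller. Describing PGI-S by visit without a model would be a legitimate alternative, provided that the sections agree and Visit 5 is named as the value of interest.
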